7.2 Demographics

Descriptive statistics of baseline demographic variables (e.g.; race and ethnic origin, height, weight, BMI, and age at randomization) will be tabulated.

In addition, for age strata and trial site, the as-randomized stratification factors (according to the actual randomization) and the actual stratification factors (according to the eCRF demographic data), will also be summarized.

7.3 Medical History

Medical history will be coded according to the Medical Dictionary for Regulatory Activities (MedDRA) using the version effective at trial start or later. The version of MedDRA will be documented. Medical history will be tabulated by System Organ Class sorted alphabetically and Preferred Term sorted in decreasing order of frequency. Medical history will only be tabulated for the mITT analysis set.

Medical history will be listed by treatment group and subject number for the mITT analysis set.

7.4 Menstrual History

The average duration of the menstrual cycle (days) will be tabulated.

7.5 Reproductive History

The following data on reproductive history following natural conception obtained at the screening visit will be tabulated: Number of subjects with at least one previous clinical pregnancy, number of clinical pregnancies per subject, number of subjects with at least one live birth, and number of live births per subject. In addition, the number of fetuses on a clinical pregnancy level and the outcome

on a fetus level (live birth, still birth, ectopic pregnancy, miscarriages by trimester, and terminations) will be tabulated.

Information on reproductive history will be listed by treatment group, subject number and previous clinical pregnancy from natural conception number for the mITT analysis set.

7.6 Infertility History

The following data on infertility history obtained at the screening visit will be tabulated: The primary reason for infertility, (all applicable) reasons for infertility, and duration of infertility (months).

The following data on previous fertility treatment cycles obtained at the screening visit will be tabulated: Number of subjects with at least one previous fertility treatment cycle, number of previous fertility treatment cycles per subject, number of subjects with at least one positive β hCG, number of positive β hCG per subject, number of subjects with at least one clinical pregnancy, number of clinical pregnancies per subject, number of subjects with at least one live birth, number of live births per subject. In addition, the type of treatment (OI/IUI/Both, assisted reproductive technology [ART]), and medications used on the cycle level, the number of fetuses on the clinical pregnancy level and the outcome on the fetus level (live birth, still birth, ectopic pregnancy, miscarriages by trimester, and terminations) will be tabulated.

Information on previous fertility treatment cycles will be listed by treatment group, subject number, and previous fertility cycle number for the mITT analysis set. The listing will include information on the start date, type of treatment, medication used, β hCG assessment, clinical pregnancy assessment, and outcome for each fetus.

7.7 Vital Signs

Blood pressure (systolic and diastolic), pulse, and temperature measured on stimulation day 1 will be summarized.

Vital signs on stimulation day 1 will be listed as part of the safety listings (Section 10.2.7.4).

7.8 Physical Examination

Each category of the physical examination is evaluated as normal, abnormal not clinically significant, abnormal clinically significant, or not done. Physical examinations at screening will be summarized by category.

Physical examinations with abnormal findings at screening will be listed as part of the safety listings (Section 10.2.8).

7.9 Endocrine Parameters

Blood samples will be collected for analysis of the following endocrine parameters: AMH, FSH, hCG, LH, E2, and P4. The baseline values will be calculated as described in Section 1.1.1 and summarized as described in Section 1.2.1.

Endocrine parameters will be listed as part of the safety listings (Section 10.2.10.4).

7.10 Gynecological Examination

Each category of the gynecological examination is evaluated as normal, abnormal not clinically significant, or abnormal clinically significant. Gynecological examination at screening will be summarized by category.

Gynecological examination with abnormal findings will be listed as part of the safety listings (Section 10.2.9).

7.11 Follicles

The number of follicles at baseline will be summarized.

7.12 Endometrial Thickness

The endometrial thickness at baseline will be summarized.

7.13 **Prior and Concomitant Medication**

Prior and concomitant medication will be coded using the World Health Organization (WHO) Drug Reference List. They will be summarized by Anatomic Therapeutic Chemical (ATC) classification 1st level (alphabetically) and ATC classification 2nd level (in decreasing order of frequency). These medications will be tabulated separately for:

- 1) Prior medication; i.e. medication taken exclusively prior to treatment (i.e.; with stop date/time before date/time of first IMP administration);
- 2) Concomitant medication; i.e. medication taken during the treatment period (i.e.; medication that was not stopped before date/time of first IMP administration and not started after the end of trial).

If the timing of the dose of a concomitant medication cannot be established in relation to the administration of IMP, it will be considered as concomitant medication.

Prior and concomitant medication will be listed by treatment group and subject number for the mITT analysis set.

8 Exposure and Treatment Compliance

Summaries will be produced for the mITT, PP, and Safety analysis sets. In the case that the Safety analysis set is identical to the mITT analysis set, presentations will use the mITT and PP analysis sets. For NIMP used prior to randomization (i.e.; oral contraceptives and GnRH agonist), a summary will be created that uses all screened subjects that received the corresponding NIMP.

8.1 Extent of Exposure

For any IMP or NIMP, duration of treatment (days) is defined as the number of days from first exposure to the day of last exposure (both inclusive).

Listings associated with the IMP and NIMP summaries will be presented.

8.1.1 IMP

Exposure to MENOPUR liquid or MENOPUR powder will be summarized by treatment group as the duration of stimulation, the total dose, the maximum and minimum daily doses, and the average daily dose defined as the total dose administered divided by the number of stimulation days. Frequency tables will be included to describe the duration of treatment by categories (<7, 7-8, 9-10, 11-12, and \geq 13 days).

Investigator-requested decreases and increases of the IMP dose will be captured during the stimulation period. The requested dose change (decrease / increase / no change) on stimulation day 6 will be tabulated. Furthermore, the total number of dose increase requests and dose decrease requests per subject will be tabulated.

8.1.2 NIMPs

Oral Contraceptives

The total dose and duration of treatment will be summarized.

GnRH Agonist

The total dose and duration of treatment will be summarized. In addition, the summary of the starting day of the GnRH agonist, relative to the last day of oral contraceptive use, will be presented.

hCG

The number of subjects that had hCG administered as well as the total dose administered for those subjects that had hCG administered will be summarized.

Luteal Phase Support

Ferring Pharmaceuticals

The total dose, average total daily dose, the duration of treatment, and the number of subjects that stopped due to menstrual bleeding will be summarized.

8.1.3 Treatment Compliance

Subjects that deviate from the planned treatment will be listed, including non-compliance to both IMP and NIMP.

9 Efficacy

9.1 General Considerations

The presentation of results for each analysis set will proceed as outlined in Section 1.2. Summaries will be made using all subjects, subjects in the <35 years age strata, and subject in the ≥35 years age strata.

9.1.1 Analysis Sets

All primary and secondary efficacy analyses will be conducted for the mITT analysis set. Furthermore, for the primary endpoint, sensitivity analyses will be conducted for the PP and ITT analysis sets as appropriate.

9.1.2 Analysis Methods

Because randomization is stratified by age strata and center, all statistical analyses of efficacy endpoints will incorporate fixed effects for both age strata and center. Except when specifically stated otherwise, all confidence intervals will be 2-sided 95% confidence intervals.

For the primary endpoint and other continuous secondary endpoints (excluding endocrine labs), an ANOVA model will be used and, in SAS, the confidence interval for the treatment difference may be produced either through an LSMEANS statement (with the PDIFF option) or an appropriately formulated ESTIMATE statement. Within-treatment group confidence intervals will also be produced using an LSMEANS statement.

For secondary pregnancy endpoints and other binary secondary endpoints, the Mantel-Haenszel method will be used to combine risk differences across the age strata and center stratification variables to produce the common risk difference. The common risk difference and associated confidence interval will be reported.

Recruitment within strata will be assessed. In the case where one or more strata have too small of a membership to perform inference, centers will be pooled together. Centers with the smallest membership will be pooled together into one or more pooled centers until inference is possible, taking care that no pooled center contains a membership larger than the median enrollment among the remaining centers and the pooled center(s).

9.2 Primary Endpoint

The primary endpoint is defined as the number of fertilized (2 pronuclei [2PN]) oocytes at 19 ± 2 hours after insemination. In addition to the primary endpoint analysis, a frequency table with subjects grouped according to their number of fertilized oocytes will be prepared using these categories: ≤ 2 , 3-5, 6-10, 11-15, and ≥ 16 2PN.

9.2.1 Primary Endpoint Analysis

The primary objective of the trial is to demonstrate the non-inferiority of MENOPUR liquid versus MENOPUR powder with respect to the number of fertilized oocytes in women undergoing

controlled ovarian stimulation. The null hypothesis is that MENOPUR liquid is inferior to MENOPUR powder where the non-inferiority limit for the difference between treatments (MENOPUR liquid minus MENOPUR powder) is set as -1.60. Therefore, the non-inferiority hypothesis to be tested for the primary endpoint will be:

 $H_0: \mu_{MENOPUR \ liquid} - \mu_{MENOPUR \ powder} \leq -1.60$

against the alternative

 $H_1: \mu_{MENOPUR \ liquid} - \mu_{MENOPUR \ powder} > -1.60$

where $\mu_{MENOPUR \ liquid}$ and $\mu_{MENOPUR \ powder}$ denote the mean numbers of fertilized oocytes in subjects treated with MENOPUR liquid and MENOPUR powder, respectively.

The null hypothesis (H_0) will be tested against the alternative by constructing a 2-sided 95% confidence interval for the difference in the least squares mean number of fertilized oocytes between the two treatment groups. If the lower-limit of the 95% confidence interval is greater than the non-inferiority limit (-1.60), the null hypothesis will be rejected and it will be claimed that MENOPUR liquid is non-inferior to MENOPUR powder with respect to the number of fertilized oocytes.

Due to the expected large sample size, the primary endpoint will be analyzed using an ANOVA model. The model will include the treatment group, the age strata, and the center as factors. The least squares mean estimate of the treatment difference in the number of fertilized oocytes and the associated 95% confidence interval will be derived as described in Section 9.1.2. For subjects who do not have any oocytes retrieved, or do not have fertilization assessment due to early withdrawal, or any other reason, the number of fertilized oocytes will be considered as zero.

If the 95% confidence interval for the treatment difference not only lies above the non-inferiority limit (-1.60) but also above zero then there is evidence of superiority in terms of statistical significance at the 2-sided 5% level. With evidence of superiority, the corresponding 2-sided p-value will be reported. There is no need for a multiplicity adjustment since it is a simple closed test procedure.

The primary endpoint analysis will be conducted for the mITT population.

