4 SELECTION OF TRIAL POPULATION

4.1 Trial Population

4.1.1 Inclusion Criteria

To be eligible for participating in the trial, subjects must satisfy the following criteria:

- 1. Signed informed consents, prior to any trial-related procedure.
- 2. Females between the ages of 18 and 42 years. The subjects must be at least 18 years (including the 18th birthday) when they sign the informed consent and no more than 42 years (up to the day before the 43rd birthday) at the time of randomization who desire pregnancy.
- 3. Body mass index (BMI) between 17.5 and 38.0 kg/m² (both inclusive) at screening.
- 4. Regular menstrual cycles of 24 to 35 days, presumed to be ovulatory.
- 5. Documented history of infertility for at least 12 months before randomization for women ≤ 35 years or for at least 6 months for women ≥ 36 years. Women with documented bilateral tubal occlusion or male factor infertility requiring the use of donor sperm established as a cause of infertility are eligible at diagnosis.
- 6. Early follicular phase (cycle day 2-4) serum FSH level between 1 and 12 IU/L (results obtained within 3 months prior to randomization).
- 7. Serum Anti-Müllerian hormone (AMH) level greater than 1.0 ng/mL at screening (central laboratory).
- 8. Male partner with semen analysis that is at least adequate for ICSI at screening or within 6 months prior to the screening date. Partners with severe male factors requiring invasive or surgical sperm retrieval may not be used. Use of donor sperm is allowed.
- 9. At least 1 cycle with no fertility medication immediately prior to screening.
- 10. Hysterosalpingography, hysteroscopy, or saline hysterosonogram documenting uterine anatomy appropriate for ART at screening or within 12 months prior to screening.
- 11. Transvaginal ultrasound documenting presence and adequate visualization of both ovaries, without evidence of clinically significant abnormality (e.g., endometrioma ≥3 cm, no dermoid cysts) and normal adnexa (e.g., no hydrosalpinx) at screening. Both ovaries must be accessible for oocyte retrieval.
- 12. Total testosterone, prolactin, and thyroid-stimulating hormone (TSH) within the normal limits for the clinical laboratory or considered not clinically significant by the investigator at screening or within 12 months prior to screening. *Note*: Subjects with high TSH levels who receive replacement therapy and are considered adequately controlled can be enrolled at the discretion of the investigator.

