6.1 Screening and Downregulation

6.1.1 Screening

Potential participants will be scheduled to come to the clinic for the screening assessments. Screening must be initiated within 90 days before stimulation day 1.

The following procedures / assessments must take place during the screening period:

- Signed and dated written informed consent must be obtained, and a copy provided to the subject, before any trial-related examinations
- Allocate a screening number
- Check the inclusion and exclusion criteria (those which are possible to check at screening)
- Demographics
- Medical history
- Menstrual history
- Reproductive history
- Infertility history
- Vital signs
- Complete physical examination (including height, weight, and BMI calculation)
- Gynecological examination
- Urine pregnancy test must be negative
- Blood collection for central laboratory analysis of:
 - Clinical chemistry and hematology parameters
 - AMH [*note*: the results must be available prior to start of downregulation due to inclusion criterion 7]
 - Anti-MENOPUR antibodies [exclusively used to re-establish the anti-drug antibody analytical assays]
- Recording of use of any concomitant medication within the last 3 months prior to signed informed consent (except medication used in previous infertility treatment cycles which will be recorded as part of the infertility history)
- Recording of adverse events (from time of signed informed consent)

Subjects considered eligible for the trial, based on the inclusion and exclusion criteria assessed at this time point, may proceed with downregulation.

In case of positive findings of HBsAg, HCV or HIV antibody tests obtained at screening, it is the investigator's responsibility to ensure that standard reporting and referral procedures at the sites are

Date: 14 Oct 2019 E-Study Protocol-21539; Ver. 6.0 Supersedes: 5.0

Page 48 of 103

followed in line with local regulations.

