6.2 Stimulation

6.2.1 Stimulation Day 1

Subjects will attend the stimulation day 1 visit within 3 days of confirmed downregulation.

Supersedes: 5.0 Page 49 of 103

The following must take place prior to randomization:

- Ensure that the subject is still eligible for participation in the trial
- Check those inclusion and exclusion criteria that were not possible during screening
- Urine pregnancy test must be negative
- Transvaginal ultrasound of uterus and ovaries (number and size of follicles)

If the subject fulfills all inclusion and no exclusion criteria, she will proceed to randomization:

• Randomization, i.e. assignment to the lowest available subject number and thereby allocation to either MENOPUR liquid (including Placebo to MENOPUR powder) or MENOPUR powder (including Placebo to MENOPUR liquid).

The following must take place after randomization but before administration of the first dose of IMP (MENOPUR liquid and Placebo to MENOPUR powder or MENOPUR powder and Placebo to MENOPUR liquid):

- Vital signs
- Blood collection for central laboratory analysis of:
 - Endocrine parameters (AMH, FSH, hCG, LH and P4)
 - Anti-MENOPUR antibodies

Once the above assessments have been completed, the following must be performed:

- Preparation and dispensing of IMP according to randomization and instruct the subject on how to administer the IMP, the subject will self-inject the IMP at home. The IMP should be injected in the lower part of the abdomen.
- Administration of IMP (MENOPUR liquid and Placebo to MENOPUR powder or MENOPUR powder and Placebo to MENOPUR liquid depending on randomization) [self-injection at home]. The starting dose of 225 IU must be maintained for 5 days.
- Hand out the diary to the subject. The subject must be instructed to assess and record injection site reactions immediately, 30 min and 24 hours after each IMP administration throughout the entire stimulation period.
- Dispensing and administration of GnRH agonist (LEUPROLIDE ACETATE) at a reduced dose of 0.05 mL (250 µg)/day [self-injection at home]
- Recording of use of any concomitant medication
- Recording of adverse events

Date: 14 Oct 2019 E-Study Protocol-21539; Ver. 6.0 Supersedes: 5.0

Page 50 of 103

6.2.2 Stimulation Day 6

The following must take place at stimulation day 6:

- Transvaginal ultrasound of uterus and ovaries (number and size of follicles)
- Blood collection for central laboratory analysis of:
 - Endocrine parameters (FSH, hCG, LH, E2 and P4)

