9.1 Determination of Sample Size

The present trial is a pharmacodynamic comparison of a marketed product to a new formulation of the same. With 188 subjects per treatment group, the trial has at least 85% power to demonstrate the non-inferiority of MENOPUR liquid to MENOPUR powder in the number of fertilized oocytes at the 1-sided significance level of 0.025. This is based on the results for MENOPUR powder from the COMBINE trial conducted in a similar setting (GnRH agonist protocol, MENOPUR starting dose of 225 IU for the first five days, insemination by ICSI etc.) and in a similar population (infertile women between 18 and 42 years). The mean (SD) of the number of fertilized oocytes were 7.88 (5.15) with similar results in the two age groups (7.92 in the <35 years age group vs. 7.80 in the ≥35 years age group). The non-inferiority margin of -1.60 will retain 80% of the expected comparator effect.

After adjusting for 5% missing data, approximately 400 subjects will be randomized (1:1) into this trial, stratified by trial site and age (<35years and ≥35 years).

A blinded sample size reassessment will be done when data on the primary endpoint are available for 70% of the planned subjects or when 300 subjects are randomized, whichever comes first. The sample size reassessment will be done without breaking the blind and without inflating the type I error of the trial, in line with current regulatory guidelines. The expected maximum number of subjects to be randomized is 500 (250 subjects per treatment group), corresponding to a blinded one-sample (both groups pooled) standard deviation estimate of 5.8 and 85% power.

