1.1 Definitions/ Abbreviations

1.1.1 Definition of Terms

Terms	Definitions
Baseline	The last available assessed value prior to the first exposure to IMP.

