Subject disposition with respect to the start of the COVID-19 pandemic trial hold will be tabulated and listed using the ITT analysis set. Subject disposition will be summarized by whether a subject had exited the trial before or after the start of the COVID-19 pandemic trial hold. Of the subjects that had not yet exited the trial, the subject status (i.e.; not yet recruited, in screening, or randomized) will be summarized.

Subjects that were in screening but had not yet been randomized prior to the COVID-19 pandemic trial hold were considered screen failures. Subjects that were screen failed due to the COVID-19 pandemic trial hold could re-enter the trial, beginning again the screening process. All subjects that were screen failed due to the COVID-19 pandemic trial hold will be listed along with an indicator of whether the subject re-entered the trial or not. Those subjects that re-entered the trial will have two screening identification numbers. Both identification numbers will be included in the listing.

For subjects that were already randomized but had not yet exited the trial at the start of the COVID-19 pandemic trial hold, the last visit completed prior to the trial hold will be summarized.

A detailed listing of selected trial assessments will be created. Included will be an indicator of whether the corresponding visit took place, an indicator of whether the visit was expected to occur before, during, or after the COVID-19 pandemic trial hold, and an indicator of whether the missingness was due to the COVID-19 pandemic.

5 **Protocol Deviations**

The rating of protocol deviations as 'minor' and 'major', as well as the criteria for major protocol deviations with the implication of exclusions from the per-protocol (PP) analysis set will be decided on the basis of a blinded review of data before declaration of clean file and lock of database.

The list of major protocol deviations will be detailed and documented in the clean file document prior to database release. Major protocol deviations will be summarized and listed by subject.

Major protocol deviations, such as significant non-compliance with the IMP regimen, NIMP regimens, or other serious unforeseen deviations that may affect the conclusions for the primary endpoint of the trial, will lead to exclusion of data from the PP analysis set. Other protocol deviations will not lead to the exclusion from the PP analysis set.

Protocol deviations due to COVID-19 will be listed.

6 Analysis sets

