9.2.2 Sensitivity Analyses

Four sensitivity analyses will be conducted. The first two sensitivity analyses will repeat the primary analysis but will use the ITT and PP analysis sets.

The third sensitivity analysis will repeat the primary analysis using the mITT analysis set, but will apply a different method of imputation for missing data. The primary analysis treats all missing primary endpoints as having observed zero 2PN. There are instances, however, where the number

of 2PN for a subject with a missing primary endpoint could theoretically have been greater than zero. Such instances may include: withdrawal of consent, being lost to follow-up, having the study terminated by the sponsor, not attending key visits, due to the COVID-19 pandemic trial hold, or other reasons that would cause a subject with a potential non-zero 2PN count to have a missing value. The temporal nature of the above stated reasons for missing a non-zero 2PN count are such that a subject would need to have taken one or more doses of IMP and have a missing primary endpoint. A sensitivity analysis for the primary endpoint will be performed by using the multiple imputation approach which could impute a non-zero value for missing primary endpoints where it can be reasonably expected that the true value would have been non-zero. The following steps will be taken to implement the multiple imputation method:

- Imputation phase An ANOVA model with factors for treatment group, age strata, and center will be fitted to data from subjects in the mITT analysis set, less those subjects with missing primary endpoints. For each missing primary endpoint, a total of 1000 draws will be made from a normal distribution that is characterized by the estimated parameters from the fitted model and the factor values associated with the missing record. A total of 1000 complete datasets will be constructed.
- Analysis phase Each of the 1000 complete datasets will be analyzed using the ANOVA model described in Section 9.1.2.
- Pooling phase The estimated mean differences and standard errors from the analysis phase will be combined using Rubin's formula (Rubin 1987):

$$m_{MI} = \frac{1}{1000} \sum_{i=1}^{1000} m_i$$

$$se_{MI} = \sqrt{\frac{1}{1000} \sum_{i=1}^{1000} se_i^2 + \left(1 + \frac{1}{1000}\right) \left(\frac{1}{1000 - 1}\right) \sum_{i=1}^{1000} (m_i - m_{MI})^2}$$

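### Efficiency option, not an error: the valid primary ANOVA leaves out screening AMH, which eligibility requires for every randomized subject

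*SAP*

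**What the plan says.** The primary model in SAP section 9.2.1 contains treatment and the two stratification factors: "The model will include the treatment group, the age strata, and the center as factors". SAP section 9.1.2 sets the same rule for all efficacy analyses, because randomization is stratified by age and center. Protocol section 9.6.2 has no patient-level covariate either. None of the four sensitivity analyses in SAP section 9.2.2 adds one, and the imputation step uses the same terms: "An ANOVA model with factors for treatment group, age strata, and center will be fitted".

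AMH is collected before randomization. Protocol section 4.1.1, criterion 7, requires "Serum Anti-Müllerian hormone (AMH) level greater than 1.0 ng/mL at screening (central laboratory". Protocol section 6.1.1 adds that "the results must be available prior to start of downregulation due to inclusion criterion 7". A second AMH sample is taken on stimulation day 1, "after randomization but before administration of the first dose of IMP" (Protocol section 6.2.1).

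For the primary endpoint, AMH appears only in a descriptive subgroup table by day 1 level (end of SAP section 9.2.2). The endocrine models in SAP section 9.3.5 do adjust for a log-transformed baseline value, so the SAP already uses that technique elsewhere.

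**The concern.** Non-inferiority is decided on the lower limit of one confidence interval, so the residual variance bears directly on the chance of success. Of the factors in the model, age explains almost nothing on the planning data: Protocol section 9.1 reports the comparator mean "with similar results in the two age groups (7.92 in the <35 years age group vs. 7.80 in the ≥35 years age group". Meanwhile a continuous baseline value, available by eligibility for every subject, stays out of the model.

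If AMH is related to the number of fertilized oocytes within strata, the planned interval is wider than it needs to be. No false claim can result; what is at stake is an avoidable share of the risk of missing non-inferiority when the two formulations are in fact equivalent.

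**Working it through.** **Inputs.** From Protocol section 9.1 and SAP section 3.2: SD 5.15, margin 1.60, one-sided alpha 0.025, 188 per arm for at least 85% power, about 400 randomized (200 per arm), up to 25 centers (Protocol section 3.2). True difference 0, as in SAP Appendix 1. The correlation r between log screening AMH and the 2PN count, within treatment and strata, is **not in the documents**; 0 to 0.5 is assumed.

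**1. The plan's own figure.** Noncentrality = 1.60 / (5.15 × √(2/n)), with 2n − 2 degrees of freedom. Power is 84.999% at n = 187 and 85.2% at n = 188, so the stated 188 reproduces.

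**2. What age explains.** The largest possible share of variance, with the two age groups equal in size, is 0.25 × (7.92 − 7.80)² / 5.15² = 0.0036 / 26.5 = 0.014%.

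**3. Effect of adding AMH.** Residual SD = 5.15 × √(1 − r²). Power is from the noncentral t with 200 per arm and about 372 degrees of freedom. Half-width = t × residual SD × √(2/200).

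| r (assumed) | Residual SD | Power, 200 per arm | 95% CI half-width | n per arm for 85% |
|---|---|---|---|---|
| 0 | 5.15 | 87.3% | 1.01 | 188 |
| 0.1 | 5.12 | 87.6% | 1.01 | 186 |
| 0.2 | 5.05 | 88.6% | 0.99 | 180 |
| 0.3 | 4.91 | 90.1% | 0.97 | 171 |
| 0.4 | 4.72 | 92.2% | 0.93 | 158 |
| 0.5 | 4.46 | 94.7% | 0.88 | 141 |

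At r = 0.3 the chance of missing non-inferiority falls from 12.7% to 9.9%.

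**4. If center also explains variance.** The table assumes center explains none. If it explained 10% (assumption), power would be 90.4% without AMH, 91.5% at r = 0.2 and 92.8% at r = 0.3.

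**5. Attenuation.** Missing endpoints are scored zero, and cycles cancelled for excessive response also become zeros. A simulation of 1,000,000 draws (negative binomial with mean 7.88 and SD 5.15, linked to AMH by a Gaussian copula, 5% random zeros, power evaluated at SD 5.15) gave:

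| r before | Top 2% of responders set to zero | Top 5% set to zero |
|---|---|---|
| 0.29 | r = 0.22, power 88.9% | r = 0.17, power 88.2% |
| 0.48 | r = 0.37, power 91.6% | r = 0.29, power 89.9% |

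The shares of zeros are assumptions.

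**6. After reassessment.** At 250 per arm and SD 5.8, power is 86.8% without AMH and 89.7% at r = 0.3.

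**7. Cost if AMH is useless.** At r = 0 the expected variance factor is about 1 + 1/371 = 1.0027, or about 0.1 point of power.

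**The case against.** The strongest reply is that nothing is broken. The ANOVA is valid, meets its power target, and follows a coherent rule: adjust for what the randomization was stratified on. Age is in the model for that reason, not for precision, so its small explained variance is no criticism. This stands, and it is why the point is an option only.

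The benefit also rests on a correlation the documents do not give. At r of 0.1 to 0.2 the gain is 0.3 to 1.3 points, from a base already above 85%. Two further features could weaken r: eligibility removes AMH at or below 1.0 ng/mL, and dose may be adjusted by follicular response from day 6. Removing the lowest 10–20% of AMH values (assumption) in the top-2% simulation lowers 0.22 to 0.16–0.18 (power 88.1–88.3%) and 0.37 to 0.27–0.31 (89.6–90.3%). If r is read as the correlation among eligible subjects, truncation is already included. A single log-linear term may also fit poorly if the highest responders are scored zero. All of this limits the size of the gain; none of it makes adjustment harmful.

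The SAP did consider AMH for this endpoint, in the day 1 subgroup table. That table is descriptive and does not narrow the primary interval. Finally, a second departure from the protocol model, after SAP version 2.0, needs justification. That is a real administrative cost, though SAP section 13 already records a change to this same model (center from random to fixed).

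**Conclusion.** The point holds as an efficiency option. The planned analysis is correct and adequately powered, but it does not use a pre-randomization value that every eligible subject has. With 200 per arm, adjustment would add between nothing and 7.4 points of power (94.7% − 87.3%) over assumed r of 0 to 0.5, with an interval up to 13% narrower. In the zero-coding simulations the gain is 0.9 to 4.3 points (88.2% to 91.6%, against 87.3%). These figures rest on SD 5.15, a true difference of 0 and, except where stated, no variance explained by center.

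The trade is asymmetric: about 0.1 point is lost if AMH carries no information. In a linear model the adjusted contrast estimates the same mean difference, so the hypotheses and the margin are unaffected. Confidence in the size of the benefit is moderate at best, because r is unknown.

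**What to change.** Before unblinding:

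- **Model.** Add log-transformed screening AMH (central laboratory) as a covariate in the primary ANOVA (SAP sections 9.1.2 and 9.2.1) and in the ANOVAs for oocytes retrieved and number of blastocysts. State whether the other endpoints sharing that model (follicle parameters, good-quality blastocysts) follow.
- **Which AMH.** Use screening rather than day 1, because it precedes randomization and is required for eligibility. Declare this an exception to the baseline definition in SAP section 1.1.1, "The last available assessed value prior to the first exposure to IMP", which would select day 1.
- **Imputation.** Add the same term to the imputation model in SAP section 9.2.2, so that it stays aligned with the analysis model, as version 2.0 intended.
- **Data rules.** SAP section 4 notes, for subjects screened again after the COVID-19 hold, that "Those subjects that re-entered the trial will have two screening identification numbers"; use the AMH from the screening that led to randomization. If screening AMH is missing, use the day 1 pre-dose value.
- **Record.** Enter the change in SAP section 13 and keep the current ANOVA as a supportive analysis.

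The sample size and the blinded reassessment need no change: the reassessment uses the raw SD and so would not credit the gain, which is conservative. The cost is one covariate in two models, two data rules and one justified entry in section 13, with no new data, visits or subjects. If the blind has already been broken, the adjusted result should be supportive only.
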